 - 3.3.5 Magnetic Resonance Imaging (MRI)(60 minutes). This pre-operative scan will help rule out intracranial abnormalities that might explain the patient's level of treatment resistance or preclude the patient from surgery. During this scan, we will also acquire diffusion tensor imaging (DTI) to assess white matter tract integrity and resting BOLD functional MRI data to assess regional connectivity.
 - 3.3.6 Neuropsychological testing (4 hours). A comprehensive neuropsychological battery will be administered by a trained psychometrist under the supervision of a board-certified neuropsychologist. This battery will take approximately 4 hours to

complete but can be done over more than one day if needed to prevent patient fatigue. The study will be performed prior to surgery and repeated at the end of 6 months of active stimulation

3.3.7 **Behavioral Activation:** In an effort to provide rehabilitation to our patients, behavioral activation therapy will be performed. There will be 2-4 sessions pre-op to establish a relationship with the patient. Therapy will begin post operatively when stimulation is started and will occur weekly for approximately 30 weeks.

3.4 **Mechanism of Action Studies.** To help assess mechanism of action (MOA) of DBS for TRD, several MOA experiments will be performed throughout the study beginning in the pre-operative evaluation period. All of the following will be repeated 1 month after surgery during acute DBS testing and again after 1,3, and 6 months of active DBS. :

3.4.1 **Emotional response testing with psychophysical measures.**

Eye-Tracking and Pupilometry: Eye-tracking will be used to measure the visual attention of the participant. The participant sits in front of a computer monitor and simply watches as pictures or sounds are presented. While they view the image or screen, a light beam is used to track the position and size of the pupil and cornea over time in order to estimate position of gaze.

3.4.1.1.1 *Emotional Pictures:* Emotional pictures will be selected from the International Affective Picture System, a standardized, widely available dataset, normed for content and emotional valence (IAPS; Lang, Bradley, and Cuthbert, 2008).

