7.0 Open Stimulation Phase (4-30 weeks post-op)

7.1 Clinical Assessments. During this phase, patients will return every two to four weeks for clinical assessments to include:

- 7.1.1 HDRS
- 7.1.2 HAS
- 7.1.3 MADRS
- 7.1.4 YMRS
- 7.1.5 BDI

- 7.1.6 BAI
- 7.1.7 IDS-SR
- 7.1.8 DAS
- 7.1.9 DOTS-R
- 7.1.10 BHS
- 7.1.11 Q-LES-Q (every 4 weeks)
- 7.1.12 HLQ (every 4 weeks)
- 7.1.13 TAS
- 7.1.14 C-SSS
- 7.1.15 PGI-S
- 7.1.16 PGI-I
- 7.1.17 CGI-S
- 7.1.18 CGI-I
- 7.1.19 Medication log
- 7.2 Behavioral Activation Therapy: Patients will begin BA with the onset of stimulation. There will be a maximum of 30 sessions over the course of the first 6 months.
- 7.3 Emotional response testing #3-4: Patients will return for repeat testing at 1 month and 3 months of DBS. SCR and activity will be monitored continuously for the first month using the Q-Sensor mobile wrist sensor, 3-D accelerometer and Garmin mobile GPS devices. Weekly testing will be performed monthly for months 2-6.
- 7.4 EEG #3 and #4: EEG will be repeated at 1 month, 3 months of DBS.
- 7.5 End of Phase MOA Assessment. At the end of this 24 Week phase, patients will be evaluated as follows (see above for details):
 - 7.5.1 Neuropsychological testing #2
 - 7.5.2 Emotional response testing, actigraphy, GPS logging and EEG #5.
- 7.6 Programming Adjustments. Initial stimulation settings will be 130 Hz, 91 μ s pulse width, 4mA monopolar bilateral stimulation (one contact per electrode array per side). Every 4 weeks, after the clinical evaluation, a decision will be made whether to continue at these settings or make an adjustment. Adjustments will be made based on whether a patient is considered IMPROVED (>10% change in the 17-item HDRS score from the previous assessment and/or at least minimally approved on the CGI-I), UNCHANGED (\leq 10% change in the 17-item HDRS score from the previous assessment and/or unchanged on the CGI-I) or WORSE (>10% increased in the 17-item HDRS score from the previous assessment and at least minimally worse on the CGI-I) using the following algorithm:
 - 7.6.1 If IMPROVED, make no change and re-assess in 4 weeks.
 - 7.6.2 If UNCHANGED or WORSE, go through the following sequence of steps:
 - 7.6.2.1 Increase amplitude to 6 mA and reassess in 4 weeks.
 - 7.6.2.2 Increase amplitude to 8 mA and reassess in 4 weeks.
 - 7.6.2.3 Re-evaluate contact location and consider a contact switch; remain at 8 mA; re-assess in 4 weeks.

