9.2.3 **Specific Aim 1.** We will record all surgical complications in addition to any other adverse events in order to get a reasonable estimate of the risks of the treatment. We will examine specific complication rates in addition to rates of "any" adverse event. We will separately document serious adverse event rates. If possible, we may also do a formal statistical comparison of these sample rates to those associated with DBS surgery in other disorders to determine if the sample rates are comparable. Rates of the first occurrence of all adverse events and device and procedure related adverse events within 24 Weeks following the initial bilateral implants will be summarized along with exact one-sided 95% upper confidence bounds. Similar analyses will be conducted for serious adverse events.

9.2.4 **Specific Aim 2.** We will estimate of the 24 Week response and remission rates; we will quantify the magnitude of the response using repeated measures analysis of variance on the depression scores (HDRS-17) comparing the levels at baseline with those after 24 Week of open DBS treatment.

9.2.5 **Specific Aim 3.** This aim is exploratory and will assess for intraoperative electrophysiological changes associated with stimulation at specific DBS contacts.

9.2.6 **Secondary Aim 1.** The purpose of this maintenance phase will be to attempt to quantify the level of treatment (dose) that is sufficient to sustain the antidepressant effect.

9.2.7 **Secondary Aim 2.** Analyses will include evaluating a variety of measures, including demographics, clinical characteristics, brain morphology and cognitive function, as possible mediators of the antidepressant effect over time. This will be formally carried out in two ways: 1) by comparing these measures in 6 month responders and nonresponders using appropriate two-sample tests (e.g, t-tests for continuous data, chi-square for categorical data) and 2) by using longitudinal analysis to see if either baseline measures of these variables or changes in these variables with treatment are significantly associated with the change in depressive symptoms over time. This can be performed using repeated measures analysis of covariance, or more simply, using linear regression predicting the change in depression (pre-post). Given the nature of the study these analyses will be underpowered but will provide useful data for future comparative trials.

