9.2.8 **Secondary Aim 3.** Analyses will evaluate EEG, emotional reactivity and psychophysiological variables over time, as possible mediators of the antidepressant effect. This will be formally carried out in two ways: 1) by comparing these measures in 6 month responders and nonresponders using appropriate two-sample tests (e.g, t-tests for continuous data, chi-square for categorical

data) and 2) by using longitudinal analysis to see if either baseline measures of these variables or changes in these variables with treatment are significantly associated with the change in depressive symptoms over time. This can be performed using repeated measures analysis of covariance, or more simply, using linear regression predicting the change in depression (pre-post). Given the nature of the study these analyses will be underpowered but will provide useful data for future comparative trials.

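### Three of the four variable classes that 9.2.7 calls mediators have no reading between switch-on and week 24, and 9.2.8 does not require its mediator reading to precede the outcome

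*Combined protocol and SAP*

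**What the plan says.** Section 9.2.7 (Secondary Aim 2) will evaluate measures "including demographics, clinical characteristics, brain morphology and cognitive function, as possible mediators of the antidepressant effect over time". Section 9.2.8 (Secondary Aim 3) uses the same label: "Analyses will evaluate EEG, emotional reactivity and psychophysiological variables over time, as possible mediators of the antidepressant effect".

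Both sections give the same two methods. The first works "by comparing these measures in 6 month responders and nonresponders using appropriate two-sample tests". The second is a longitudinal analysis of whether "either baseline measures of these variables or changes in these variables with treatment are significantly associated with the change in depressive symptoms over time". On the model, the text reads "This can be performed using repeated measures analysis of covariance, or more simply, using linear regression", and the regression option is described as "linear regression predicting the change in depression (pre-post" (closing bracket omitted here). Both sections say that the analyses will be underpowered.

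On timing, 3.3.6 says of the neuropsychological battery: "The study will be performed prior to surgery and repeated at the end of 6 months of active stimulation". Section 7.5.1 places the second battery at the end of the 24-week phase. Section 7.4 says "EEG will be repeated at 1 month, 3 months of DBS", and 3.4 schedules the emotional and psychophysiological tests at the same months, with a further session at month 6.

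The Objectives word Secondary Aim 2 as a search for variables that predict response, remission and relapse. They do not mention mediation there.

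**The concern.** Calling a variable a mediator claims an order: stimulation changes the variable, and that change then alters mood. If the variable cannot be changed by treatment, or is not read between switch-on and the outcome, the data cannot speak to that order. If it is read at the same visit as the outcome, an association fits equally well with mood improvement having changed the variable.

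The protocol itself expects some influence in that second direction. In 3.4.3.2.2 the reasoning is that relief of depression will make mood regulation easier, and that this will show as greater EEG coherence after successful treatment. That path runs from mood to EEG, whereas 9.2.8 treats EEG as a possible mediator, on the path from stimulation to mood.

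Section 9.2.5 confines the analysis of Specific Aim 3 to intraoperative recordings, so 9.2.8 carries the question of mechanism under chronic stimulation. Both sections say that their results are meant to inform later comparative trials. A marker that merely follows recovery could be taken forward as a mechanism.

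**Working it through.** **Step 1. Scheduled readings of each named class against the 24-week outcome.**

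| Class | Before stimulation | On stimulation, before week 24 | At week 24 |
|---|---|---|---|
| Demographics (9.2.7) | fixed | cannot change with treatment | – |
| Brain morphology (9.2.7) | MRI at screening (3.3.5), on the day of surgery (4.1) and after surgery (5.0) | none | none |
| Cognitive function (9.2.7) | before surgery (3.3.6) | none | yes (7.5.1) |
| Clinical characteristics (9.2.7; not defined) | yes | ratings every two to four weeks (7.1) | yes |
| EEG, emotional response, psychophysiology (9.2.8) | sessions #1 and #2 | months 1 and 3 (3.4, 7.3, 7.4) | session #5 (7.5.2) |

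Patients leave hospital with the system off (6.1), so the post-operative MRI is not an on-stimulation reading. The other post-operative scan is a CT to locate the contacts (6.4). The ten-year phase (8.3) lists neither MRI nor a neuropsychological battery.

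Count: 3 of the 4 classes in 9.2.7 have no usable reading between switch-on and week 24. For morphology, change with treatment cannot be computed at all. For cognition, it can be computed only at the time of the outcome. All three classes in 9.2.8 have two on-stimulation sessions before the outcome.

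**Step 2. What the analysis text fixes.** The two-sample comparison names 6-month response status but not when the compared measure is read. The longitudinal option allows baseline values or changes, with no time point or lag. The bracketed pre-post in the regression option describes the depression change, not the candidate mediator. Neither section requires the mediator reading to come first, and neither describes an indirect-effect analysis.

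**Step 3. Why a week-24 analysis cannot show direction (illustration; all parameters assumed).** Let M be the mediator change and Y the mood change, with 1 = month 3 and 2 = month 6. The e terms are independent standard normal errors; M1 and Y1 are independent standard normal in the first two cases.

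- Mediator drives mood: M2 = 0.7·M1 + √0.51·e; Y2 = 0.5·Y1 + 0.5·M1 + 0.6·e.
- Mood drives the variable: the same equations with M and Y exchanged.
- Shared cause U (standard normal): M1 = 0.5·U + e; M2 = 0.5·M1 + 0.5·U + 0.6·e; likewise for Y.

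In the first case cov(M2, Y2) = 0.7 × 0.5 = 0.35, var(M2) = 0.49 + 0.51 = 1 and var(Y2) = 0.25 + 0.25 + 0.36 = 0.86, so the correlation is 0.35/√0.86 = 0.38. Exchanging M and Y leaves it unchanged, so the second case gives 0.38 too.

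Proportion significant at two-sided 5%, from 20,000 simulated trials per cell. The lagged test is the partial correlation of M1 with Y2 given Y1. The sizes used are 19 (section 9.2.2) and 40 (Objectives).

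| Truth | Concurrent, n=19 | Concurrent, n=40 | Lagged, n=19 | Lagged, n=40 |
|---|---|---|---|---|
| Mediator drives mood | 36.3% | 68.2% | 85.4% | 99.6% |
| Mood drives the variable | 36.5% | 68.3% | 5.0% | 5.0% |
| Shared cause | 56.8% | 89.6% | 16.3% | 32.3% |

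The concurrent test cannot tell the first two rows apart. The lagged test brings reverse causation back to its nominal 5% but does not remove a shared cause. The high lagged figures in the first row arise because the effect was built in at month 3; they are not a power claim for this trial.

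**Step 4. The plan's own figure.** The plan gives no figure for the mediator analyses. Its exploratory figure (effect size 0.68 with 19 patients, 9.2.2) reproduces as a one-sample or paired t-test: noncentrality 0.68 × √19 = 2.96, 18 degrees of freedom, power 80.0% at two-sided 5% (alpha and power assumed). It does not bear on time order.

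**The case against.** The strongest reply is that the plan does not commit itself to a concurrent analysis, and this stands. A reader might infer that the pre-post regression uses week-24 values of EEG and the other measures, so that mediator and outcome are always read together. The text does not say so: pre-post belongs to the depression change. Repeated measures analysis of covariance is listed first and could use months 1 and 3, so it would also be wrong to say that those sessions have no role. The defect is that the order is left open.

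A reader might also conclude that none of the four classes in 9.2.7 is read during stimulation. That fails for clinical characteristics, since many clinical ratings are taken every two to four weeks.

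Other replies carry part of the way. Secondary Aim 2 is about prediction, and baseline variables serve it well; this supports changing the label rather than keeping it. The aim also covers relapse, and ratings continue for ten years, so week-24 cognitive change does precede later relapse. That use is legitimate. The analyses are secondary, declared underpowered and speak only of possible mediators, and study success (9.1.6) does not depend on them, which limits the severity. But low power is a separate weakness: more patients would not reveal direction.

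Finally, a lagged analysis has limits of its own. Behavioral activation starts with stimulation (7.2), programming is reviewed every four weeks using HDRS-17 and CGI-I (7.6), and there is no control arm. This also stands.

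**Conclusion.** The concern holds in a limited form. In 9.2.7, three of four named classes cannot be shown to mediate the 24-week outcome on the protocol's own schedule; this rests on the visit schedule alone. In 9.2.8, the sessions needed for an ordered analysis are already planned, but the text permits a concurrent week-24 association, which cannot separate mediator from consequence.

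The wider inference, that no mechanism analysis of EEG, emotional response or psychophysiology could be informative, is not supported, because the month-1 and month-3 sessions allow an ordered one. Even so, a lagged association would be suggestive only.

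The simulated percentages depend on the assumed coefficients of 0.5 and 0.7 and on mood being measured without error. The equality of the two directions follows from giving both the same strength. This is a worthwhile, inexpensive correction to exploratory analyses, and it does not touch the primary efficacy or safety conclusions.

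**What to change.** In 9.2.7, call demographics, brain morphology and pre-operative cognition baseline predictors, in line with the Objectives. Report week-24 cognitive change as a concurrent correlate of the 24-week outcome; it may also be used to predict later relapse.

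In 9.2.8, state the lead analysis as:

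HDRS-17 at week 24 = b0 + b1 × (M at month k − M at reference) + b2 × HDRS-17 at month k, for k = 1 and k = 3,

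with b1 the quantity of interest. The reference should be the pre-operative session. Session #2 qualifies only for recordings made with stimulation off: the Schema places it in the off phase, but 3.4 and 3.4.3 tie it to acute stimulation testing, and 3.4.3.2.1 plans both on and off recordings. Report month-6 comparisons as concurrent association only.

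The cost is SAP wording and one analysis of data already scheduled. Fewer variables can be called mediators, and some power may be lost in an analysis already described as underpowered. The report should state that a shared cause is not excluded in a single open-label arm with behavioral activation and HDRS-guided programming.

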10.0 Data and Safety Monitoring

10.1 Expected Side Effects/Potential Adverse Events. The complications of DBS surgery are well established and relate to surgical complications at the time of implantation and secondary complications due to failure of the device, infection or stimulation of structures adjacent to intended target structures. Effects of acute and chronic Cg25-DBS in depressed patients are largely unknown. No unanticipated psychiatric, neurological or other medical adverse effects have been observed in 20 patients studied to date in Toronto, or the 23 patients implanted thus far as part of this protocol. Three out of the first five patients in the Toronto series developed local wound infections; however, these infections occurred in the context of two separate surgeries separated by one week with externalization of the electrodes for testing. This prompted a switch to performing both surgical procedures at the same time and no infections have occurred since (in the next eight patients). Risks of general anesthesia are well-known include a less than 1/200,000 risk of death. Based on data collected to date on DBS in Parkinson's Disease patients, the rate of serious surgery-related adverse events (e.g., hemorrhage, seizures, hemiparesis/hemiplegia, serious infection) is approximately 10%. The rate of all serious adverse events is approximately 53%, and the rate of all (including minor) adverse events is approximately 88%.

10.2 Adverse Event Rates Leading to Study Discontinuation. Based on the DBS in PD event rates listed above, study discontinuation will be considered in the following situations:

- 10.2.1 If the serious surgery-related adverse event rate is more than double the above rate (>20%), the study will be halted and the DSMB will carefully review the data to determine if the risks of the study outweigh benefits.
- 10.2.2 If the rate of all serious adverse events is greater than the rate for PD (>53%), the study will be halted to allow the DSMB to carefully review the data to determine if the risks of the study outweigh benefits.
- 10.2.3 If the rate of all adverse events is greater than the rate for PD (>88%), the study will be halted to allow the DSMB to carefully review the data to determine if the risks of the study outweigh benefits.

10.3 Data and Safety Monitoring Board (DSMB). In light of the limited experience with this procedure in psychiatric patients, we will use the Data Safety Monitoring Board (DSMB) for the Department of Psychiatry and Behavioral Sciences as a third-party oversight committee.

- 10.3.1 DSMB Composition. The DSMB for this study will consist of the Clinical Research Oversight Committee members including co-chairs [name]. and [name]., [name], L.C.S.W and [name], M.A. Should the DSMB require additional specialized expertise to evaluate safety issues related to the performance of this study, a relevant specialist will be consulted.
- 10.3.2 Frequency of meetings/review. The frequency of DSMB review for this protocol will follow recommendations from the IRB based on the assessed risk status of the study. Currently, it is expected that the DSMB will meet quarterly.
- 10.3.3 This protocol will be submitted to the DSMB simultaneously with this initial submission to the Emory IRB. The DSMB will review the research protocol and plans for data and safety monitoring. Twice per year, the DSMB will review a report from the study's data manager that includes the following information: the number of participants who signed consent forms for the study and were subsequently randomized to study arms, the number of post-randomization dropouts, the reasons for withdrawal from the study, and any safety concerns, adverse events, an up-to-date consent form, and measures taken to protect confidentiality (e.g., data and tape storage, use of coded ID numbers, etc.). The DSMB will also review the Principal Investigator's summary of any new data or evidence that might alter the risk/benefit ratio for participating in the study (e.g., newly published studies, etc.). After reviewing this information, the DSMB will issue its own report summarizing any serious and unexpected adverse events or other unanticipated problems that involve risk to study participants, and whether these appear related to the study-based interventions or research assessment protocols.
- 10.3.4 There will be regular, ongoing communication between the PI, Emory's IRB, and the DSMB. The PI will take responsibility for reporting any serious and unexpected adverse events or other unanticipated study problems to Emory's IRB within 24 hours, according to standard regulations. A copy of each report will be sent to the DSMB. Actions taken by the IRB in response to adverse event reports will be immediately reported to the DSMB, which will review all serious adverse events as they arise. DSMB reports will be shared with the IRB.
- 10.3.5 A Serious Adverse Event (SAE) in this study will be defined as an event that results in death, is life-threatening, requires hospitalization or prolongation of existing hospitalization, or results in persistent or significant disability or incapacity. The degree of probable relation between study procedures and the SAE will be carefully evaluated and documented.
- 10.3.6 Unexpected adverse events in this study will be defined as any adverse events for which the nature and severity are not consistent with expected adverse events resulting from the surgery, pre- or post-operative evaluation, or deep brain stimulation.
- 10.3.7 The DSMB will have the authority to stop the study at any point.

REFERENCES

3. American Psychiatric Association. Practice guideline for the treatment of patients with major depressive disorder (revision). *Am J Psychiatry*. Apr 2000;157(4 Suppl):1-45.
4. Fava M. Diagnosis and definition of treatment-resistant depression. *Biol Psychiatry*. Apr 15 2003;53(8):649-659.
